2.3.5.3 Barthel index

Barthel score is a continuous variable (0-100) and will be summarized using number, mean, standard deviation, median, minimum and maximum, by treatment groups. The frequency table of each class level will also be provided.

2.4 DATA PROCESSING CONVENTIONS

2.4.1 Definition of baseline

In this study, baseline values are defined as those data collected before intervention (screening visit). When multiple data collections occur during the baseline period, the final data shall prevail in principle, unless explicitly stated.

2.4.2 Missing data

We will report proportions of missing values for all collected variables where needed.

Baseline characteristics missing data will be imputed by regression interpolation as appropriate.

If there is a large number of missing data on efficacy and safety, an evaluation on the missing data should be conducted before analysis, and will propose and determine the solution before database lock.

For patients who died within the study period, the worst scores will be assigned for all not-assessed clinical outcome measures in their analyses, as follows [Table 2](#).

Table 2 The worst scores of clinical outcomes

Clinical outcomes	The worst scores
mRS	6
NIHSS	42
The Barthel index	0

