1.3 STUDY OUTCOMES

Primary outcome:

The primary outcome is the score on the modified Rankin Scale (mRS) ([Table 1 in Appendix](#)) at 90 days (± 14 days). The mRS is the preferred disability parameter for clinical trials in stroke. The mRS is an ordinal hierarchical scale incorporating six categories from 0 up to and including 5, and describes the range of disability encountered post stroke. "Death" is assigned a score of 6. Assessment of outcome on the mRS will be performed by outcome committee, blinded to the allocated and actually received treatment. Their assessment will be based on standardized reports of a telephone interview by trained research personnel who are not aware of treatment allocation.

Secondary outcomes:

- Death within 90 days (± 14 days)

- Pre-interventional recanalization
- extended treatment in cerebral ischemia scale (eTICI) score on final angiography of IAT ([Table 2 in Appendix](#))
- Recanalization rate at 24-72 hours, assessed with CTA
- Score on the NIHSS at 24±6 hours and 5 -7 days. ([Table 3 in Appendix](#))
- Final infarct volume at 5-7 days. Final infarct volume will be assessed with the use of an automated, validated algorithm. Infarct size at day 5-7 will be compared with plain computed tomography (CT) and perfusion CT results (if available) at baseline.
- Dichotomized mRS of 0-1 vs. 2-6 at 90 days (±14 days)
- Dichotomized mRS of 0-2 vs. 3-6 at 90 days (±14 days)
- Dichotomized mRS of 0-3 vs. 4-6 at 90 days (±14 days)
- Score on the EuroQol-5 dimensions-5 level (EQ5D-5L) ([Table 4 in Appendix](#)) and Barthel index (BI) ([Table 5 in Appendix](#)) at 90 days (±14 days)

Safety outcomes:

- Hemorrhages according to the Heidelberg criteria [1]
- sICH scored according to the Heidelberg criteria [2]
- Embolization in new territory on angiography during IAT
- Occurrence of aneurysma spurium
- Occurrence of groin hematoma
- Infarction in new territory at 5-7 days ([Table 6 in Appendix](#))
- Death from all causes within 90 days (±14 days)

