2.1.2.2 Secondary efficacy variables

- Death within 90 days (± 14 days)
- Pre-interventional recanalization
- eTICI score on final angiography of IAT. ([Table 2 in Appendix](#))
- Recanalization rate at 24-72 hours, assessed with CTA
- Score on the NIHSS at 24 \pm 6 hours and 5 -7 days. ([Table 3 in Appendix](#))
- Final infarct volume at 5-7 days. Final infarct volume will be assessed with the use of an automated, validated algorithm. Infarct size at day 5-7 will be compared with plain CT and perfusion CT results (if available) at baseline.
- Dichotomized mRS of 0-1 vs. 2-6 at 90 days (± 14 days)
- Dichotomized mRS of 0-2 vs. 3-6 at 90 days (± 14 days)
- Dichotomized mRS of 0-3 vs. 4-6 at 90 days (± 14 days)
- Dichotomized mRS of 0-4 vs. 5-6 at 90 days (± 14 days)
- Dichotomized mRS of 0-5 vs. 6 at 90 days (± 14 days)

- Score on the EQ5D-5L and Barthel index at 90 days (± 14 days)

Pre-interventional recanalization: Recanalization rate (eTICI 2b, 2c or 3) before patients received mechanical intra-arterial treatment according to the DSA.

Recanalization rate at 24-72 hours: defined as the proportion of patients in whom recanalization as determined on 24-72 hours CTA is achieved.

eTICI score: eTICI assessment will be performed post IAT. The eTICI classification includes 0, 1, 2a, 2b, 2c and 3 ([Table 2 in Appendix](#)).

NIHSS score: The NIHSS is an ordinal hierarchical scale to evaluate the severity of stroke by assessing a patient's performance. Scores range from 0 to 42, with higher scores indicating a more severe deficit ([Table 3 in Appendix](#)). NIHSS assessment will be performed at baseline, 24 ± 6 hours post operation and 5-7 days post operation.

The EuroQoL 5-dimensions 5-level (EQ-5D-5L) questionnaire is a standardized measure of health outcome that has been used extensively in patients with stroke ([Table 5 in Appendix](#)). EQ5D-5L assessment will be performed at 90 ± 14 days post operation.

The Barthel index (BI) is an ordinal scale used to measure performance in 10 activities of daily living (ADL). Test scores range from 0 to 100, with higher scores indicating better performance in these daily activities ([Table 4 in Appendix](#)). BI assessment will be performed at 90 ± 14 days post operation.

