2.3.5 Analysis of quality of life

2.3.5.1 NIHSS score

NIHSS (0-42) score and change from baseline are continuous variables and will be presented with summary statistics, including number of subjects, mean, standard deviation, median, minimum and maximum, by treatment groups and by visits. Repeated measures of variance analysis will be used to explore the impact of treatment grouping visits and NIHSS baseline levels.

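### The NIHSS score of 42 for deaths is not limited to deaths before the visit, and the point mass at 42 is analysed with means and ANOVA

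*SAP*

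**What the plan says.** SAP section 2.4.2 states: "For patients who died within the study period", "the worst scores will be assigned for all not-assessed clinical outcome measures". Its Table 2 sets the NIHSS value at 42. The trigger is death at any time in the study, and nothing in the rule refers to the date of the assessment that was missed. Section 2.4.3 (time window) is marked not applicable, so it adds no limit.

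The NIHSS outcome in section 1.3 is "Score on the NIHSS at 24±6 hours and 5 -7 days". All-cause death, in the same section, is followed to 90 (±14) days.

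Section 2.1.2.2 describes the scale thus: "The NIHSS is an ordinal hierarchical scale to evaluate the severity of stroke". Section 2.3.5.1 nevertheless says "NIHSS (0-42) score and change from baseline are continuous variables and will be presented with summary statistics", and the one between-group method it names is this: "Repeated measures of variance analysis will be used to explore the impact of treatment grouping visits and NIHSS baseline levels".

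**The concern.** There are two separate problems.

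**The trigger.** Both NIHSS visits fall in the first week, while the death that activates the rule may come up to three months later. Take a patient alive on day 6 whose NIHSS was not done and who dies on day 60. The rule scores this patient 42 on day 6, the same as someone already dead on that day. That value is false: a later death is recorded as an early neurological deficit. The mRS does not share the problem, because death is itself a category of that scale and it is read at day 90. The Barthel index is also a day-90 measure.

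**The analysis.** Giving the worst score to a patient already dead at the visit is a defensible composite. It does create a cluster at the ceiling of the scale, far from the other scores. Means and ANOVA are sensitive to such a cluster, so a real difference among the other patients may be hidden, or a difference in mortality may be read as points of neurological recovery. Deaths also accumulate between the two visits, so visit effects in the repeated-measures model would partly reflect mortality.

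Neurological recovery on the NIHSS is part of the tertiary objective (section 1.2) and is a listed secondary outcome.

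**Working it through.** **Inputs from the SAP.** There are 318 patients per arm (section 1.4: 710 × 0.85 = 603.5; 603.5 / 0.95 = 635.3, taken to 636). Assumed control mortality at 90 days is 21% (section 1.4). The SAP gives no NIHSS mean, SD, effect or power and no mortality at 24 hours or day 5-7, so there is no NIHSS figure of its own to reproduce.

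**Assumptions.** NIHSS in patients without an assigned 42 has mean 10 and SD 8. The true difference among them is 2 points (10 versus 8). One visit is compared, two-sided 0.05, without baseline adjustment.

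**1. Trigger.** One living patient wrongly set to 42 moves an arm mean by (42 − true score)/318.
- True score 12: 30/318 = 0.09 points.
- True score 25: 17/318 = 0.05 points.

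Even ten such patients, all in one arm, would move its mean by only 0.5 to 0.9 points. The SAP gives no basis for their number.

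**2. Point mass at 42, equal in both arms.** With fraction f at 42 and mean m among the rest, the arm variance is (1 − f)·8² + f(1 − f)·(42 − m)².
- At f = 5%, m = 10: 60.8 + 48.6 = 109.4, SD 10.5, variance ratio 109.4/64 = 1.7.
- At f = 10%, m = 10: 57.6 + 92.2 = 149.8, SD 12.2, ratio 2.3.

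Averaging the two arms' variances (m = 10 and m = 8) gives the pooled SD below. The mean difference shrinks to 2(1 − f). Power is Φ(difference / (SD·√(2/318)) − 1.96). At 5% this is 1.90 / (10.61 × 0.0793) = 2.26, and Φ(0.30) = 0.62. The simulated columns come from 4,000 trials with skewed (gamma-shaped) scores.

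| f in each arm | Pooled SD | Mean difference | Power, formula | Simulated, t-test | Simulated, rank test |
|---|---|---|---|---|---|
| 0% | 8.0 | 2.00 | 0.88 | 0.91 | 0.99 |
| 2% | 9.2 | 1.96 | 0.77 | 0.78 | 0.99 |
| 5% | 10.6 | 1.90 | 0.62 | 0.62 | 0.98 |
| 10% | 12.5 | 1.80 | 0.44 | 0.46 | 0.95 |

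A second simulation with negative binomial scores gave 0.63 versus 0.97 at 5% and 0.45 versus 0.93 at 10%. With mean 8 and SD 7, the t-test gave 0.96, 0.85, 0.66 and 0.46 over the same four rows, and the rank test stayed at 0.99 or above.

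**3. The SAP's mortality as an anchor.** A common odds ratio of 1.163 turns 21% mortality into odds of 0.2658/1.163 = 0.2286, which is 18.6%. If 10%, 25%, 50% or 100% of these deaths produced a 42, formula power would be 0.80, 0.71, 0.61 or 0.52, against 0.88 with none.

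**4. Unequal deaths.**
- 10% versus 5% at 42, no difference among the rest: 0.05 × 32 = 1.6 points of mean difference. The t-test is significant in 43% of runs and the rank test in 20%.
- 5% versus 8%, with more deaths in the arm that is 2 points better: 11.60 − 10.72 = 0.9 points. t-test power is 0.18 and rank-test power 0.89.
- 10% versus 5%, in the direction of the effect: 13.2 − 9.7 = 3.5 points. t-test power is 0.98.

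With equal point masses and no true difference, the error rate of both tests stays near 5%.

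**The case against.** The strongest objection concerns attribution. A reader might infer that the power loss in the table is the consequence of the loose trigger. It is not. Those figures describe the whole cluster at 42, most of which would probably be true early deaths, and correcting the trigger leaves those deaths in place. The trigger produces only the small shifts in step 1. Section 1.5 calls the NIHSS at these visits routine and assigns it to certified assessors, so living but unassessed patients should be few. If they are balanced between arms, the comparison hardly moves. All of this stands.

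Part of the gap between the two tests comes from the assumed skewness and not from the rule: with no one at 42 the rank test already has 0.99 against 0.91. This stands too, although the gap widens to about 0.36 at 5% (0.98 − 0.62).

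The SAP may also leave room for a better method. Section 2.3.2.2 allows a non-parametric test or a transformation for continuous secondary outcomes, and its list of those outcomes is not exclusive. Section 2.3.5.1 reports the median as well. Section 2.4.2 provides for a review of extensive missing data before database lock. But section 2.3.5.1 refers to none of these for the between-group comparison, the median is descriptive only, and the missing-data review does not change the rule for deaths.

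Finally, the ANOVA is worded as exploratory, and survivors alone are not a randomised comparison. Both points are fair. They limit the stakes and support keeping a worst score for patients who have died, but they do not justify applying it to patients still alive at the visit.

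**Conclusion.** The trigger is wrong as worded: it can place a 42 at a visit the patient survived. Its effect is of unknown size and probably small, 0.05 to 0.09 points on an arm mean per patient for assumed true scores of 25 to 12.

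The second defect is the more consequential. A mean-based comparison is poorly suited to an ordinal scale with a cluster of deaths at its ceiling. Under the stated assumptions and equal early deaths, its power falls from about 0.9 to about 0.78, 0.62 and 0.45 at 2%, 5% and 10%, while a rank test keeps about 0.93 or more. The NIHSS mean, SD, effect and early death rates are all assumed, and baseline adjustment is not modelled.

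Two stronger readings are not supported. One is that the rule always weakens the comparison: when deaths run clearly in the direction of the effect, it strengthens it, with break-even near 5% versus 3.1% or 10% versus 6.5%. The other is that the trial's main conclusion is at risk: the primary mRS analysis and the sample size of 636 do not depend on the NIHSS.

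**What to change.** - In section 2.4.2, assign NIHSS 42 only when death preceded the scheduled NIHSS assessment. Treat every other unassessed NIHSS as missing, and say how missing values are handled.
- In section 2.3.5.1, compare the arms at 24 hours and at day 5-7 with a proportional odds model or a rank-based analysis, adjusted for baseline NIHSS and the primary covariates. Keep means and SDs as description.

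The cost is a clause of wording and one model per visit, of a type section 2.3.2.1 already uses for the mRS. The downside is that the effect is an odds ratio or a rank-based measure and not a difference in NIHSS points. The change should be made before database lock.

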2.4.3 Time window

Not applicable.

2.4.4 Unscheduled visits

Not applicable.

2.4.5 Centers pooling

Unless specifically specified, this study will not consider the center effect, so it will not pool and analyze the data of each study center.

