1.1 STUDY DESIGN AND RANDOMIZATION

This is a multicenter prospective randomized clinical trial with open-label treatment and blinded outcome assessment (PROBE). The study will run for 4 years in intervention centers. Randomization will be stratified by center. The treatment allocation is 1:1 for:

- Direct IAT (MT),
- IVT followed by IAT (IVT plus MT)

[figure not shown]

Figure 1 Patient flow in the trial

The intervention group will undergo immediate intra-arterial treatment (IAT) using a stent retriever, as recommended by the steering committee. Patients in the control group will receive alteplase intravenous treatment (IVT) (0.9 mg/kg with a maximum dose of 90 mg), followed by IAT using a stent retriever.

Local application (intra-arterial) of alteplase is allowed in any of the patients included in the DIRECT-MT if necessary. Patients pre-treated with IVT should not receive more than 30mg alteplase during intra-arterial treatment. Delivery of alteplase in shots of 5 mg in 5-10 minutes intervals is recommended. An equivalent dose of 400,000 U urokinase, delivered in shots of 50.000 - 100.000 U, in 5-10 minutes time intervals, is also accepted as escape medication in individual cases. If successful reperfusion (eTICI 2b-3) is not achieved in the direct MT group, IVT with 0.9 mg/kg may be initiated if the 4.5 hour window or maximum dose is not exceeded.

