2.3.2.1 Primary efficacy outcome

The primary effect parameter is the common odds ratio, which will be estimated by ordinal logistic regression (proportional odds model), which represent the shift on the full distribution of the modified Rankin Scale at 90±14 days. Estimations will be adjusted by known prognostic variables such as age (median), pre-stroke mRS (continuous), time from symptom onset to randomization (" \leq Q1", ">Q1, \leq Q2", ">Q2, \leq Q3", ">Q3"), stroke severity (NIHSS, median) and collaterals (Grade 0-1, Grade 2-3). Adjusted and unadjusted estimations and their corresponding 95% confidence intervals will be reported. To assess non-inferiority of direct MT compared to IVT with MT, we will assess whether the 95% CI lower bound of the adjusted common odds ratio cross our pre-specified non-inferiority boundary (0.8).

The following SAS procedure will be used for ordered logistic regression analysis (proportional odds model):

```
Proc logistic data=XXX;  
Class TRT FactorA ...;  
Model mRS90= TRT AGE FactorA ...;
```

Run;

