2.3.2.2 Secondary efficacy outcome

Continuous secondary efficacy outcomes are mainly infarct size at 5-7 days after operation and recanalization rate before intervention as well. Analysis for these outcomes will be mainly based on statistical descriptions. Where necessary, analysis of variance or corresponding non-parametric test will be used for between-group comparisons. If applicable, the linear regression analysis will be used with adjustment for the same covariate variables as the primary outcome analysis. When deemed necessary, log or other common transformation of non-normal distribution will be used.

Categorical secondary outcomes include mortality at 90 days after operation, recanalization rate at 24-72 hours, dichotomized mRS score at 90 days after operation (0-1 vs. 2-6, 0-2 vs. 3-6, 0-3 vs. 4-6), successful recanalization before and after Mechanical thrombectomy (MT), and eTICI score at MT final angiography. Chi-square test will be used for comparison between the two groups, or Fisher's exact test will be used for comparison when applicable. The categorical secondary outcomes will be analyzed by logistic or ordered regression analysis to provide a common odds ratio and its confidence interval, if applicable. The adjustment method is the same as that in the primary outcome analysis.

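### Randomisation is stratified by centre but the primary model leaves centre out: a minor mismatch with the design, worth at most about one point of power

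*SAP*

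**What the plan says.** Section 1.1 states: "Randomization will be stratified by center". Centre is the only stratification factor the SAP names, and allocation is 1:1.

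Section 2.3.2.1 defines the primary analysis as a proportional odds model: "Estimations will be adjusted by known prognostic variables such as age (median), pre-stroke mRS (continuous), time from symptom onset to randomization", followed by "stroke severity (NIHSS, median) and collaterals (Grade 0-1, Grade 2-3". Centre is not listed. The SAS model line begins "Model mRS90= TRT AGE FactorA" and ends in an ellipsis, with no centre, strata or random term. The verdict comes from this model: "we will assess whether the 95% CI lower bound of the adjusted common odds ratio cross our pre-specified non-inferiority boundary (0.8".

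Section 2.4.5 adds: "Unless specifically specified, this study will not consider the center effect, so it will not pool and analyze the data of each study center".

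For the categorical secondary outcomes, 2.3.2.2 says: "The adjustment method is the same as that in the primary outcome analysis".

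**The concern.** The trial balances treatment within centres and then analyses the data as if centres did not exist. If outcome differs between centres, this has two consequences. First, the odds ratio is non-collapsible, so the model without centre estimates a common odds ratio (cOR) slightly nearer 1 than the within-centre one. Second, stratified allocation removes between-centre variation from the treatment comparison but the model does not know this, so its standard error is slightly larger than the estimator's true sampling SD.

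Both affect the one number that decides the trial, the lower confidence bound against 0.8. In a non-inferiority trial a shift towards 1 deserves a check, because at the margin it moves the estimate in the favourable direction.

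The text leaves some room: the covariates in 2.3.2.1 are introduced as examples, the model line is open-ended, and 2.4.5 allows for exceptions. No section uses that room. Read literally, 2.4.5 settles the matter against centre and gives no reason.

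**Working it through.** **Inputs from the SAP.** Section 1.4: control mRS 0 to 6 of 3/9/21/18/22/6/21% (sum 100%), cOR 1.163, margin 0.8, two-sided alpha 0.05, power 80%, 710 patients, 15% reduction, 5% dropout, final 636. Section 1.1: 1:1 allocation, stratified by centre.

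**The plan's own figure.** Whitehead's formula for the proportional odds model is N = 12(z₀.₉₇₅ + z₀.₈₀)² / [ln(1.163/0.8)² × (1 − Σp̄³)], where p̄ is the mean of the two arms' mRS distributions.

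- Numerator: 12 × (1.960 + 0.842)² = 94.19.
- ln(1.163/0.8)² = 0.3741² = 0.1400, and 1 − Σp̄³ = 0.965.
- N = 697, against the stated 710 (within 2%). Power at 710 is 80.7%.
- 710 × 0.85 = 603.5, and 603.5/0.95 gives 636 after rounding up, as stated.

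The number analysed is therefore 636 × 0.95 = 604.

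**Main simulation.** 40,000 trials per setting, 604 patients, control distribution as in 1.4. Assumptions not in the SAP: 40 centres of unequal size (gamma(1.5) weights), permuted blocks of 4 within centre, between-centre log-odds SD of 0.2, 0.4 or 0.6 after adjustment, and one prognostic score (log-odds SD 1.0) in both models. Non-inferiority is declared if log cOR − 1.96 SE > log 0.8.

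| Between-centre SD 0.2 / 0.4 / 0.6 | Without centre | Random centre intercept |
|---|---|---|
| Estimate, true within-centre cOR 0.80 | 0.802 / 0.805 / 0.811 | 0.801 / 0.801 / 0.801 |
| Estimate, true within-centre cOR 1.163 | 1.162 / 1.161 / 1.154 | 1.163 / 1.165 / 1.162 |
| Mean model SE at 1.163 | 0.1461 / 0.1461 / 0.1460 | 0.1461 / 0.1461 / 0.1463 |
| Sampling SD at 1.163 | 0.1451 / 0.1429 / 0.1398 | 0.1458 / 0.1457 / 0.1462 |
| Model SE relative to sampling SD | +0.7 / +2.2 / +4.4% | +0.2 / +0.3 / +0.1% |
| False non-inferiority at 0.80 (Monte Carlo SE 0.08) | 2.48 / 2.57 / 2.54% | 2.48 / 2.57 / 2.52% |

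The power gain at 1.163 from adding centre is 0.03 / 0.35 / 0.84 points (paired Monte Carlo SE 0.04 / 0.07 / 0.09). With no centre variation, power is 72.3% without centre and 72.4% with it, and false non-inferiority is 2.5% in both. With 20 centres and SD 0.4, the estimate at 0.80 is 0.804 without and 0.800 with centre, and the gain is 0.42 points. Power is below 80% in both models because the 15% reduction has been spent on a smaller sample. This does not affect the comparison.

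**Why the two effects cancel.** Take SD 0.6 without centre, borrowing the SE and SD from the 1.163 row. The lower bound clears 0.8 when a standard normal variable exceeds (1.96 × 0.1460 − ln(0.811/0.80))/0.1398 = (0.2862 − 0.0137)/0.1398 = 1.949, a probability of about 2.6%. The shift towards 1 helps a false claim. The overstated SE hinders it by about as much.

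**Second simulation.** 12,000 trials per setting, 20 or 40 centres, covariate log-odds ratio 0.8 per SD, blocks of 4. Centre enters as a fixed effect, with centres of fewer than 5 patients merged.

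- Without centre, a true 0.80 is estimated as 0.803–0.804 at SD 0.3, 0.808 at SD 0.5 and 0.817–0.818 at SD 0.8.
- The gain in power is 0.2 to 1.1 points; the largest is at SD 0.8 with 40 centres (71.1% to 72.2%).
- False non-inferiority is 2.45 to 2.67% without centre and 2.46 to 2.85% with it (Monte Carlo SE about 0.14).

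A further run of the model without centre (4,000 trials per setting, 40 centres, SD 0.6) gave about 0.811 for 0.80 and 1.153 for 1.163. Model SE was 0.146 against a sampling SD of 0.141–0.143, and false non-inferiority was 2.5–2.8%. Blocks of 8 gave the same pattern.

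**Fixed centre effects as a fallback.** In the main simulation, with centres under 10 patients merged, false non-inferiority is 2.5 / 2.6 / 2.5% and power 72.3 / 72.9 / 72.2%. Estimates lie slightly away from 1 (0.796 for 0.80; 1.167–1.170 for 1.163). Fits failed in 0–7 of 40,000 trials with 40 centres and 72–76 with 20. A limit of 5 patients raises this to 38–243 and 1,022–1,217.

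**The case against.** The best defence is that 2.4.5 makes an open, prespecified choice with almost no consequence. False non-inferiority does not change, the interval does not narrow, and the smallest power gain is within simulation error. The 0.84-point gain needs a between-centre SD of 0.6, which means odds differing exp(2 × 1.96 × 0.6) = 10.5-fold between centres at the 2.5th and 97.5th percentiles. The omission is, if anything, slightly conservative. The attenuation is also a difference of target rather than an error, since the SAP nowhere says 0.8 was set for a within-centre cOR. A mixed model with a fallback adds complexity, and fixed effects bring a distortion of their own.

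Most of this stands, and it is why the point is minor. It does not remove the mismatch: the SAP states a stratified design, sets the stratification factor aside and gives no reason. On the target, 2.3.2.1 already applies 0.8 to an adjusted cOR, so centre adds one more conditioning variable and no new kind of estimand. The fixed-effect distortion is the reason to put the random intercept first. The SE mismatch might have depended on small blocks, but blocks of 8 show the same pattern.

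One reservation remains open. No binary outcome was simulated, so carrying the centre term over to sparse secondary outcomes, such as pre-interventional recanalization, is untested.

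**Conclusion.** The concern holds as a minor one. Centre defines the randomisation strata, is absent from the primary model and is expressly set aside in 2.4.5. If centres differ, the model without centre reports a cOR slightly nearer 1 than the within-centre value (0.802–0.811 for 0.80) with an SE 0.7–4.4% too large. Adding centre removes the attenuation and makes the SE match the design, for a gain of at most about one point of power. It does not protect against false non-inferiority, because there is no inflation to protect against. If centres do not differ, nothing is gained or lost.

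The mismatch is plain from the text. Its size rests on an assumed number of centres, centre sizes, block size, between-centre SD and covariate strength, none of which the SAP gives.

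**What to change.** Replace the sentence in 2.4.5 with:

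> *The primary adjusted proportional odds model includes a random intercept for centre, the stratification factor. If it does not converge, centre enters as a fixed effect after all centres with fewer than 10 analysed patients are merged into one group; if that group still has fewer than 10, it joins the smallest remaining centre. The model without centre is reported as a sensitivity analysis.*

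Add to 2.3.2.1:

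> *The 0.8 margin is applied to this adjusted (within-centre) common odds ratio.*

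The SAS code in 2.3.2.1 must change to a procedure that fits a cumulative-logit mixed model. Because 2.3.2.2 copies the primary adjustment, the centre term carries over to the secondary models. The SAP should say so, and should say what applies if a sparse binary outcome cannot support it.

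The cost is SAP wording and a different procedure. Data collection and sample size do not change. If the sponsor prefers to leave centre out, 2.4.5 should give the reason and the model with centre should be the sensitivity analysis.
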